## **Specific Aims**

The 2008 Federal Physical Activity Guidelines recommend that adults obtain at least 150 minutes of moderate physical activity per week to maintain and improve health. Based on these guidelines, sedentary individuals may adopt a structured aerobic exercise program (e.g. 30 minutes of treadmill exercise 5 days per week) to meet these recommendations. While this approach is beneficial, the potential exists for aerobic training programs to be optimized by also addressing the low levels of physical activity outside of structured exercise training sessions (Non-Ex PA). Three large randomized controlled trials performed in our laboratory suggest that previously sedentary adults participating in aerobic exercise training still exhibit low levels of Non-Ex PA (e.g. 4,500 to 6,000 steps/day). In addition, our group has published data suggesting that obese postmenopausal women participating in aerobic exercise training with high levels of Non-Ex PA had greater reductions in waist circumference and body weight compared to those with low levels of Non-Ex PA. Our results are supported by several epidemiological studies demonstrating that the amount physical activity below the threshold of moderate to vigorous intensity has clinical benefits (lower body weight, waist circumference, and 2-hour fasting glucose) independent of the amount of moderate to vigorous physical activity performed. Therefore, a physical activity program composed of 1) aerobic training and 2) increasing the amount of Non-Ex PA may represent a more complete and clinically effective physical activity intervention compared to a program focused on aerobic training only. However, to date, a prospective study examining the effectiveness of an intervention of this nature has not been performed.

**The Intervention Composed of Aerobic Training and Non-Exercise Physical Activity (I-CAN) study will investigate the effects of aerobic exercise training and increasing Non-EX PA on waist circumference, weight, and other cardiovascular disease risk factors in a prospective pilot trial.** We will randomize sedentary (<6,500 steps per day) obese adults (N= 45) with at least one additional cardiovascular risk factor to a: (1) structured aerobic exercise program with no intervention on Non-Ex PA (AERO group, N=15); (2) structured aerobic exercise program with the additional goal of increasing Non-EX PA (AERO-PA group, N=15), or (3) a control group (CON, N=15) for 6 months. Exercise groups will participate in the same aerobic training program (50 to 75% VO2 max), designed to be consistent with public health recommendations of 150 minutes per week of moderate physical activity. Non-Ex PA in the AERO group will be tracked throughout the entire 6 month intervention with pedometers capable of counting steps, but not displaying them to the participant (blind mode capable). The AERO-PA group will progressively increase Non-Ex PA (1,000 to 3,000 steps per day above baseline levels) throughout intervention using pedometers. The AERO-PA group will also participate in lifestyle counseling grounded in the principles of the social learning and behavioral change theories to determine/reinforce strategies to increase Non-Ex PA. The primary outcome measure will be change in waist circumference following the intervention. The study results will be used to determine the efficacy/feasibility of the intervention, and power a larger trial as an R01 application.

## **Specific Aims:**

To test the hypothesis that:

- Aerobic exercise training and increasing Non-EX PA will reduce waist circumference to a greater extent compared to the aerobic exercise training alone and the control group.
- Aerobic exercise training and increasing Non-EX PA will reduce weight and fat-mass to a greater extent than aerobic exercise training alone and the control group.

**Additional Aims:** We will also evaluate the effect of the intervention on fitness and insulin sensitivity

## 1. Background and Significance

The 2008 Federal Physical Activity Guidelines  recommended that adults participate in at least 150 minutes/week of moderate physical activity.

Substantial evidence exists that physical activity programs consistent with these recommendation have profound health benefits for sedentary adults , and a structured aerobic exercise training program (e.g. 30 minutes, 5 times a week) represents an effective strategy to meet these recommendations . However, there is potential

for aerobic exercise programs to be optimized. The results of several published studies indicate that the amount of physical activity performed outside training (Non-Ex PA) remains low (similar to pre-training levels) in previously sedentary adults participating in aerobic exercise training . **Therefore, this low amount of Non-Ex PA may represent an additional intervention target to use along with aerobic exercise.**

Hamilton et al.  has described (in reference to sitting, Figure 1.) that ample opportunities exist for sedentary behavior even individuals who are presumed to be "physically active." For example, a training session of 45 minutes represents less than 3% of waking hours leaving the remaining 95% at risk for potential sedentary behaviors.

Definitions for physical activity terminology used in the present proposal:

**Non-Exercise Physical Activity (Non-Ex PA):** Free-living physical activity not performed during an aerobic exercise training program (pedometer-determined) or below the threshold of moderate to vigorous physical activity (accelerometer-determined).

**Dose of exercise training:** Amount of kilocalories expended during an aerobic exercise training intervention relative to body weight. Used to standardize training for caloric expenditure across participants. Expressed as kilocalories per kg per week (KKW).

[figure not shown]

Figure 1. Hamilton et al. *Current Cardiovascular Risk Reports* 2008. Opportunities for sitting during the day for an individual who exercises 45 minutes

This relationship, along with the declining levels of occupational,  transportation-related , and physical activity in the home  has led some researchers to question the extent to which a bolus of exercise training (i.e. 30-45 minutes of aerobic exercise) mitigates the risk associated with low levels of physical activity or prolonged periods of inactivity throughout the day . Thus, a physical activity program composed of aerobic training only, while beneficial, could be optimized by also increasing the amount of Non-Ex PA outside of training sessions. However, to date, no prospective studies exist combining aerobic exercise training and increasing Non-Ex PA. If clinically effective, this intervention could represent a more complete approach in treating obese sedentary adults compared to aerobic training alone, which may have a greater overall effect in reducing central adiposity, weight, and subsequently other cardiovascular disease risk factors. The core concepts of this intervention (aerobic exercise training and high Non-Ex PA) are transferable and feasible in clinical, public health, and exercise training settings. This may have important clinical implications as the majority of adults in the United States (58%) do not obtain the recommended amount of physical activity, which is especially prevalent in obese (64%) individuals .

**1.1 Non-Ex PA in Aerobic Exercise Training Studies:** Adults participating in aerobic training still exhibit low levels of Non-Ex PA (4,500-6,000 steps/day). Our research team has monitored Non-Ex PA in three large randomized controlled exercise training trials . Pedometers were used to quantify the amount of Non Ex-PA over the course of the entire training intervention.

**Importantly, pedometers were not worn during exercise training sessions.** In the DREW (postmenopausal women, N=464) , INFLAME (adults with elevated C-reactive protein, N=162) , and HART-D (adults with type 2 diabetes, N=262)  studies, we observed no significant change in pedometer determined Non Ex-PA compared to the control group (Figure 2). This finding was consistent across studies despite differences in the duration of the

intervention (4 to 9 months), exercise training intensity (50%-85%  $\text{VO}_2$  max), and aerobic training energy expenditure (4 to 16 kilocalories per kg per week [KKW]). In the DREW trial, Non-Ex PA was not significantly different compared to control even at an exercise dose as high as 150% public health recommendations. Our findings are supported by other large randomized controlled trials such as the STRIDDE (duration: 8 months) and the STRIDDE AT/RT (duration: 4 months) studies, which report no significant change in accelerometer determined Non-Ex PA in overweight and obese middle aged adults.

**1.2 Non-Ex PA independent of MVPA (moderate to vigorous physical activity) on CVD risk factors:** Non-Ex PA is likely performed for the most part below a moderate to vigorous intensity, but contributes to total energy expenditure. Epidemiological and retrospective analyses from prospective training studies suggest that high Non-Ex PA has clinical value in promoting lower weight, waist circumference and other CVD risk factors.

**1.3 Epidemiological evidence:** Several epidemiological studies have demonstrated that physical activity below the threshold of MVPA can have a beneficial effect on CVD risk factors independent of the amount of MVPA. Specifically, Camhi et al. using NHANES data observed that accelerometer determined lifestyle physical activity (760-2,019 counts/ minute) decreased the odds of low HDL, high triglycerides, elevated blood pressure, high fasting glucose, waist circumference, and the presence of the metabolic syndrome or type 2 diabetes independent of MVPA (>2,020 counts/minute). Healy et al. found that higher amounts of accelerometer determined “light intensity physical activity” (100-1,952 counts) was associated with lower 2-hour plasma glucose levels independent of MVPA ( $\geq 1,952$  counts). Similarly, Healey et al., in a different study, found that even in adults meeting physical activity recommendations, significant dose-response associations were observed for higher waist circumference, 2- hour plasma glucose and systolic blood pressure with higher television viewing time. The authors hypothesized that the cardiometabolic consequences of high television viewing time could be due to the displacement of light intensity physical activity.

## 2. Preliminary studies:

**Non-Ex PA and Exercise Training:** Little data exist evaluating the effect of different amounts of Non-Ex PA on anthropometric or CVD risk factors in adults participating in aerobic training. Di Blasio et al. found that postmenopausal women who decreased Non-Ex PA outside of training did not have beneficial improvements in plasma low density lipoprotein and triglyceride levels compared to those that maintained or increased Non-Ex PA. Our laboratory conducted the Dose Response to Exercise in Women (DREW) study, which investigated the effects of 6 months of aerobic training at levels consistent with public health recommendations, and 50% below or 50% above those recommendations on cardiorespiratory fitness in postmenopausal women. The DREW study used pedometers to quantify the amount of Non-Ex PA outside of

[figure not shown]

Figure 2. Non-Ex PA defined as steps/day in the DREW, INFLAME, and HART-D trials. **Step counters were not worn during exercise sessions.** KKW: kilocalories per kg per week. Data are expressed as (mean  $\pm$  SD)

exercise training . Postmenopausal women with the highest amount of Non-Ex PA, while also participating in aerobic training had greater reductions in waist circumference compared to those in the lowest tertile of Non-Ex PA at all three doses of exercise training (4, 8 and 12 KKW) (Figure 3). Aerobic training with high Non-Ex PA was also associated with modest weight loss (when all exercise groups were combined and statistical models were adjusted for exercise training dose) . Higher Non-Ex PA with exercise training did not provide additional beneficial effects for the change in fitness, systolic or diastolic blood pressure. Although, we investigated women who **self-selected** to levels of Non-Ex PA outside of training sessions, our data does suggest that an intervention composed of aerobic training and increasing levels of Non-Ex PA may accelerate the improvements in waist circumference. This may have greater effects on adiposity and other CVD risk factors when Non-Ex PA is **increased** along with aerobic training.

### 3. Research Design and Methods

#### 3.1 Innovation:

The Intervention Composed of Aerobic Training and Non-Exercise Physical Activity study (I-CAN) study will evaluate for the first time a physical activity intervention composed of **structured aerobic exercise training along with a strong emphasis on increasing the amount of physical activity outside of training on waist circumference, weight and other cardiovascular risk factors training against the standard prescription of aerobic training alone**. To date, exercise training studies primarily focus on adherence to aerobic exercise and instruct participants not to alter Non-Ex PA. While studies following this model have established effectiveness in promoting favorable changes in CVD risk factors, the I-CAN study will attempt to optimize these benefits by also increasing the amount Non-Ex PA (defined as steps/day outside of training) through the use of pedometers along with structured aerobic training. The design of I-CAN is composed of several innovative features including: strict monitoring of Non-Ex PA throughout the entire 6 month intervention, behavioral support (both web-based and in-person), goals for progressively increasing Non-Ex PA with aerobic exercise training, and an equivalent dose of aerobic exercise training (designed to be consistent with public health recommendations) in the exercise groups. This could represent a practical and clinically effective approach for clinicians and trainers to further increase total energy expenditure in the treatment of obese patients. However, pilot data supporting the efficacy and feasibility of this intervention is necessary prior to implementation in a large randomized trial.

#### 3.2 Approach:

The target study population of the **I-CAN** study will be sedentary obese men and women (BMI: 30-40 kg/m^2, age 40-65 yrs). We will randomize participants to aerobic training (AERO, N=15), aerobic training and increasing Non-Ex PA (AERO-PA, N=15) group or a non-exercise control group (CON, N=15) for 6 months (24 weeks). Participants in the AERO or AERO PA groups will participate in the same structured aerobic training program 3 times per week in a laboratory setting, and wear pedometers during the entire 6 month intervention (except during structured aerobic training sessions). The AERO-PA group, in addition to aerobic training, will increase Non-Ex PA progressively from 1,000 to 3,000 steps/day above baseline from week 6

[figure not shown]

Figure 3. Swift et al. *American Journal of Preventive Medicine*. 2012. Change in waist circumference in the DREW study stratified by amount of Non-Ex PA in the 4, 8 and 12KKW

to week 24 of the intervention. The CON group will continue their current physical activity habits during the intervention. **The primary outcome measure of I-CAN is the change in waist circumference following the intervention.** Secondary measures include change in fitness, body weight, body composition (fat and lean mass), pedometer determined steps/day of Non-Ex PA during the intervention, accelerometer-determined physical activity, fasting glucose, fasting insulin and homeostatic model of insulin resistance (HOMA-IR).

**3.3 Inclusion/Exclusion Criteria:** The inclusion/exclusion criteria are summarized in Table 1. The goal of the I-CAN study is to recruit adults with moderate to high CVD risk that can safely perform the supervised aerobic training in our facility. In addition, all participants must have sufficient health to increase Non-Ex PA in their daily lives, as this will not be directly supervised by study staff. Therefore, we will recruit sedentary obese men and women (age: 40-65) with elevated waist circumference (women:  $\geq 88$  cm, men:  $\geq 102$  cm), and at least one additional CVD risk factor. Individuals with type 2 diabetes and known cardiovascular disease will be excluded due to the pilot nature of this trial, and the necessity to establish the efficacy of this intervention prior its utilization in a higher risk study population.

**Table 1. Summary of the Inclusion/Exclusion Criteria**

Inclusion Criteria for Study Participation	
Age	40-65 years of age
Sex	Men and women
Non-exercisers and sedentary/low active lifestyle	Not currently participating in aerobic or resistance exercise $\geq 20$ minutes on $\geq 3$ days per week for the last 6 months. Pedometer determined objective measurement of physical activity $\leq 6,500$ step/day
One or more of the following CVD risk factors	Triglycerides (TG) $\geq 150$ mg/dL  , HDL-C $< 50$ mg/dL, Blood pressure: systolic $\geq 130$ mmHg and diastolic $\geq 85$ mmHg or the use of BP medication, Fasting glucose: 100-125 mg/dL (type 2 diabetes is exclusionary), LDL-C $\geq 130$ mg/dL, or currently taking cholesterol lowering medications
Abdominal obesity/BMI	Waist circumference $\geq 88$ cm (women), $\geq 102$ cm (men)  ; BMI: 30-40 kg/m 
Informed Consent	The capability and willingness to give written informed consent, to understand the exclusion criteria
Exclusion Criteria	
Significant CVD or disorders	Including but not limited to serious arrhythmias, cardiomyopathy, congestive heart failure, stroke or transient ischemic attacks, peripheral vascular disease with intermittent claudication, acute, chronic or recurrent thrombophlebitis or myocardial infarction
Diabetes	Diagnosis or taking medication for type 1 or 2 diabetes and/or fasting glucose $> 125$ mg/dL
Resting blood pressure	Systolic blood pressure $> 180$ and diastolic blood pressure $> 100$  . Participants currently taking blood pressure medication (except for diuretics) can enroll in the present study
Blood lipids	Total cholesterol $\geq 240$ mg/dL, LDL-C $\geq 160$ mg/dL or TG levels $\geq 300$ mg/dL. Cholesterol medications are permitted.
Other significant medical conditions	Including but not limited to chronic or recurrent respiratory, gastrointestinal, neuromuscular, neurological, HIV or psychiatric conditions. Hospitalization for mental illness within the past 5 years or Musculoskeletal problems interfering with exercise. Autoimmune or

	collagen vascular diseases. Other medical conditions which is life-threatening or can be aggravated by exercise training
Other exclusions	Plan to be away from Pitt County area more than 2 weeks in the next 3 months. Currently or plans to become pregnant. Currently or plans to engage in dieting or a weight loss program. No home access to internet. Previous bariatric or gastric banding surgery, or weight loss medications. Non-compliance during screening in wearing pedometers or failure to document physical activity levels in the study online database.

**3.4 Primary Outcome- Waist Circumference:** We have selected waist circumference as the primary outcome measure of the I-CAN study for the following reasons: 1) Elevated waist circumference is associated with CVD risk factors, represents one of the components of the metabolic syndrome, and has incremental value in predicting CVD, diabetes and mortality risk over and above BMI. 2) Waist circumference can be feasibly evaluated in the clinical setting, which has relevance to clinicians (e.g. physicians, personal trainers, nutritionists) working with obese adults. We considered visceral fat mass by MRI as the primary measure, however, the increased burden to participants, high costs, and the fact that it is not measured in the clinical setting lead us to the decision that it was not appropriate for this pilot trial, especially since we will obtain measurements of trunk fat mass through DEXA; 3) Our retrospective published data demonstrating that high Non-Ex PA with aerobic training resulted in greater reductions in waist circumference compared to low Non-Ex PA.

**Measurement of waist circumference:** We will utilize standard operating procedures (SOPs) for assessment measures including waist circumference. Staff are tested and certified annually on the correct measurement technique. Participants will stand in a straight, upright position with the feet together with arms at their side. Waist circumference will be measured at the natural waist (midway between the inferior border of the rib cage and the superior aspect of the iliac crest) with a Gulick tape measure. Both landmarks (the inferior border of the ribcage and the superior aspect of the iliac crest) will be marked and the distance will be measured to determine the appropriate measurement site. Staff will confirm that: 1) the measurement tape remains horizontal; 2) the tape touches the entire circumference of the participant; 3) abdominal tissue is not compressed; 3) the tape measure is not within abdominal folds; 4) the measurement is taken at the end of normal respiration. The measurement will be repeated an additional time, and the reported value will be the average of these measurements. Both measurements must be within 0.5 cm to be considered acceptable for data purposes. A third measurement is required if values are > 0.5 cm. Waist circumference will be evaluated at baseline, mid-intervention, and at follow-up.

**3.5 Secondary measures:** Secondary measures include: change in fitness, body weight, body composition, pedometer determined Non-Ex PA during the intervention, accelerometer determined physical activity levels, fasting glucose, fasting insulin and HOMA-IR.

**Anthropometric & Dual Energy X-ray Absorptiometry (DXA):** Height will be measured at screening. Body weight will be evaluated using a calibrated scale (recorded to the nearest 1/10 of a kg), with the participant fasted and wearing only a hospital gown. DXA will be used to measure body composition (fat and lean mass).

**Accelerometry:** At each major assessment point, participants will wear the GT3X+ accelerometer (ActiGraph, LLC, Pensacola, Florida, USA) at their waist for seven consecutive days, 24-hrs/day. We have successfully used this 24-hour protocol in adults and find that it maximizes wear time. This accelerometer has been validated and is one of the most widely used accelerometers in research and has the capability of detecting minute-by-minute

steps (steps/min, which can be totaled to obtain steps/day) and physical activity intensity using previously validated activity count cut points . More recently, it has been used to estimate time in sedentary behaviors as time spent at < 100 activity counts/min .

**Maximal Exercise test:** Testing will be performed on a treadmill (Trackmaster 425, Carefusion, Newton Kansas) using a modified Balke protocol to determine maximal oxygen consumption (VO2 max), and the correct heart rate range for aerobic exercise training (50% to 75% of VO2 max). Participants will walk at an initial speed of 2.0 mph with 0% grade for the first 3 minutes after which the treadmill speed will increase to 3.0 mph for the next 2 minutes. The treadmill grade will be increased by 2.5% every 2 minutes until volitional exhaustion. Respiratory gases (VO2, CO2) and ventilation will be measured continuously using a True Max 2400 Metabolic Measurement Cart (Parvomedics, Salt Lake City Utah).

**Pedometer:** Pedometers will be used to determine sedentary status during screening (over the course of 7 days), and to measure Non-Ex PA during the intervention. We have selected the Lifecorder PLUS (New-Lifestyles, Lees Summit, Mo), which has a feature that does not allow the participant to see the amount of steps walked on the pedometer's display (blind display mode). This feature is ideal for the determination of sedentary status during screening, and monitoring Non Ex-PA in the CON and AERO groups. Non-Ex PA data will be downloaded directly from pedometers for data purposes. We elected to use pedometers for monitoring Non-Ex PA because accelerometers are rarely used in clinical practice. In addition, pedometers allow direct feed-back (i.e. steps/day) to participants about Non-Ex PA levels.

**Tracking dietary changes:** We will utilize the Food Frequency Questionnaire (FFQ) originally developed by Drs. Gladys Block and Linda Harlan, often referred to as the "Block FFQ" . This questionnaire collects information about eating habits over a 12-month period. The FFQ contains approximately 105 items grouped by categories and is completed for both frequency of consumption as well as portion size selections by the individual. The questionnaire, upon completion, provides estimated daily intake values for selected nutrients (kilocalories, macronutrients, and micronutrients) and provides information on food group servings. **All participants will be instructed and reminded regularly not to alter dietary habits or engage in purposeful dieting during the intervention.**

**Blood sample collection:** Trained personnel will obtain fasting venous blood samples from the antecubital site with participants in a seated position. Either 21 or 23 gauge needles will be used, depending on vascular access. Standard OSHA guidelines will be followed at all times. At baseline and follow-up, a total of 20 mL of blood will be drawn. Of this, 10 mL will be immediately sent to the Clinical Laboratory for lipid assessment, insulin and blood chemistries. Lipids and other biochemical measures will be made using standard analytic techniques. The remaining 10 mL sample will be centrifuged under refrigerated conditions, and the supernatant will be extracted, and divided into 1 mL portions. Vials of plasma (3-4), serum (2-3), and red blood cells (2-3) will be stored at -80°C for future analysis.

**3.6 Recruitment and Pre-Screening:** Study personnel will screen interested individuals over the phone based on the inclusion/exclusion criteria. Eligible individuals will be invited to attend an **orientation session**, during which study personnel will provide a presentation with detailed information about the study (structure of the study, study-related procedures, risks, benefits, etc.). Individuals interested in I-CAN following this orientation session will be consented at this time, and scheduled for run-in visits.

**Run-in visits:** The run-in period will last for two weeks in order to: 1) verify sedentary status (pedometry) and screen for other inclusion/exclusion criteria (e.g. BMI, waist circumference, blood pressure); and 2) ensure participants are able to make the time commitment to come to

to training sessions. In our past training studies, this run-in period has helped to obtain excellent training adherence by allowing potential participants to thoroughly evaluate their ability to commit to the time demands of a study. To simulate participation in the actual I-CAN intervention, run-ins will be scheduled 3 sessions per week over the course of two weeks, and duration will be similar to that of training sessions (~1 hour). During run-ins, participants will wear pedometers for 7 days, and enter information about self-monitoring into the study website (using RED Cap, described in detail below). Participants will confirm they wore the pedometer at the beginning of the day, and notate the extent of non-wear time (Figure 4). Pedometers will be worn in “blind display mode”, so the amount of steps accumulated throughout the day will not be seen by the participant. We will ask participants to employ methods to remember to wear the pedometer at the beginning of the day (placing reminders on calendars or smart phones, placing pedometer on clothes to wear). On the last run-in session, participants will meet with a trained interviewer who will use a semi-structured barriers interview, to evaluate for any major barriers to study participation or completion.

Run-in:
Information collected:

 
• Did you wear the pedometer today (yes/No)
 
• Were there any periods of time where pedometer was not worn (Yes/No)
 
• If so, please provide an estimate of the approximate time: _____
 
• Further comments: _____
 

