**Figure 4. Web-based questions to determine pedometers compliance.**

**Pedometer compliance tracking:** We will utilize RED Cap™, a secure online research database to: 1) track and monitor participant compliance wearing pedometers; and 2) record Non-Ex PA at run-in and during the intervention. Participants will be provided a unique name/password to log on to the study website. The use of RED Cap™ will allow our staff to monitor participant compliance throughout the trial in real-time. Our research team is successfully using RED Cap™ in two on-going prospective physical activity trials.

**3.7 Clinical Visits (baseline, mid-intervention, and follow-up):** We will obtain primary (waist circumference) and secondary outcome measures (DEXA, fitness, blood measures) at both baseline and follow-up (summarized in Figure 5). Pre-menopausal women will be asked to take a pregnancy test. A physician or a physician’s assistant will obtain a medical history and perform a brief medical exam. **All clinic staff measuring outcome measures will blinded to participant randomization.**

At mid-intervention (week 12), we will measure waist circumference, weight, FFQ, and accelerometry. The CON group will be scheduled for mid-intervention and follow-up visits, and will be instructed not to alter physical activity habits during the intervention. All groups will be instructed not to alter dietary habits during the study.

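### Table 1's resting blood pressure exclusion joins its two limits with 'and', so read literally a person above only one limit is not excluded before the maximal treadmill test

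*Combined protocol and SAP*

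**What the plan says.** The resting blood pressure row of the exclusion criteria in Table 1 reads "Systolic blood pressure $> 180$ and diastolic blood pressure $> 100". The rest of the row deals with blood pressure medication and adds no further limit.

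Two other exclusion rows in the table make their alternatives explicit:

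- Blood lipids: "Total cholesterol $\geq 240$ mg/dL, LDL-C $\geq 160$ mg/dL or TG levels $\geq 300$ mg/dL".
- Diabetes: "Diagnosis or taking medication for type 1 or 2 diabetes and/or fasting glucose $> 125$ mg/dL".

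The text of section 3.3 states the purpose of the criteria, which is to "recruit adults with moderate to high CVD risk that can safely perform the supervised aerobic training in our facility". It also requires that participants be healthy enough to raise their daily activity without direct supervision. Section 4 names exercise training and exercise testing as the parts of the study with the greatest safety risk.

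**The concern.** A numeric exclusion should give the same decision whoever applies it. As worded, this one requires the systolic and the diastolic limit to be exceeded together. No systolic value, however high, excludes a person whose diastolic pressure is 100 or lower, and no diastolic value excludes a person whose systolic pressure is 180 or lower.

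A reader of Table 1 has some reason to take *and* at face value, because the lipids and diabetes rows use *or* and *and/or* where one condition is enough. The result also sits oddly in the table: triglycerides of 300 mg/dL exclude a person without any other finding, but a resting systolic pressure of 200 with a diastolic of 98 does not.

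At stake is who goes on to the maximal test, for which section 3.5 says "The treadmill grade will be increased by 2.5% every 2 minutes until volitional exhaustion" and gives no blood pressure limit for starting or stopping.

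**Working it through.** The question is how two limits are joined, so the check is one of logic. S is systolic and D is diastolic pressure.

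**Rules compared**

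- As written: exclude if S > 180 and D > 100.
- With one word changed: exclude if S > 180 or D > 100.

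| Reading | S > 180 | D > 100 | Excluded as written | Excluded with *or* |
|---|---|---|---|---|
| 200/98 | yes | no | no | yes |
| 175/110 | no | yes | no | yes |
| 181/100 | yes | no | no | yes |
| 180/101 | no | yes | no | yes |
| 181/101 | yes | yes | yes | yes |
| 185/105 | yes | yes | yes | yes |
| 180/100 | no | no | no | no |
| 175/95 | no | no | no | no |

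The two rules differ exactly where one limit is exceeded and the other is not.

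**Is there another upper limit elsewhere?**

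- Table 1, risk-factor row: the figures 130 and 85 are lower limits for inclusion. Since 200 ≥ 130 and 98 ≥ 85, and 175 ≥ 130 and 110 ≥ 85, both example readings meet this criterion. They therefore count towards entry.
- Section 3.6, run-in: staff "screen for other inclusion/exclusion criteria (e.g. BMI, waist circumference, blood pressure"), which applies the Table 1 limits and adds none.
- Section 3.7: a physician or physician's assistant "will obtain a medical history and perform a brief medical exam". No blood pressure limit is given.
- Figure 5: blood pressure appears at run-in and again at the clinic evaluation, without a limit.
- Table 1, other medical conditions: the catch-all "Other medical conditions which is life-threatening or can be aggravated by exercise training" could apply, but it rests on judgement and names no value.

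No other passage supplies a single-limit rule.

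**Planned exposure**

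- Maximal test: 15 + 15 + 15 = 45 randomized participants. Figure 5 places the baseline test in the same clinic evaluation as consent for randomization, so anyone tested but not randomized would add to this.
- Supervised training (AERO and AERO-PA): 15 + 15 = 30.
- Prescribed unsupervised increases of 1,000 to 3,000 steps/day (AERO-PA only): 15.

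These counts show who is exposed to the procedures, not how many people the wording would let through.

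**Side note on consistency.** The risk-factor row also joins its two limits with *and*. An untreated reading of 150/80 meets the first (150 ≥ 130) but not the second (80 < 85), so it does not count as the blood pressure risk factor; with *or* it would. Such a person can still qualify through another listed factor, and there is no safety consequence.

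**The case against.** The strongest reply is that *and* here lists two separate exclusions. Section 3.3 uses the word that way just before the table, when it says that people with type 2 diabetes and known cardiovascular disease are left out: Table 1 gives those conditions separate rows, so either one is enough. The risk-factor row also joins systolic and diastolic limits with *and*, which suggests a habit of phrasing. On this view the row already means what the fix would say, and the fault is ambiguity rather than error.

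The practical risk is also limited. Blood pressure is checked at run-in and again at the clinic evaluation, a clinician examines each person, and the catch-all exclusion is available. For someone at 200/98 to reach the treadmill, screening staff would have to apply the strict reading and the clinician would have to let it stand.

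Much of this stands. The list reading is probably what was intended, and the safeguards reduce the chance of harm. But they do not provide a rule under which exceeding one limit is enough, and the neighbouring lipids and diabetes rows point a careful reader the other way. Two screeners could reach opposite decisions on the same person, each with support from the text.

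**Conclusion.** The concern holds. As written, the exclusion does not remove a person who exceeds only one of the two limits, and nothing else in the document sets an upper blood pressure limit before the maximal test. The conclusion rests on reading the row literally and on the document as supplied; staff instructions outside it may be clearer.

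How many people would be affected cannot be estimated, because the document gives no blood pressure distribution for the screened population. The trial's statistical validity is not in question. This is a wording fault in a safety criterion, partly covered by clinical judgement, and it should be corrected.

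**What to change.** In the resting blood pressure exclusion row of Table 1, replace *and* with *or*, so that systolic pressure above 180 or diastolic pressure above 100 excludes. This matches the form of the lipids and diabetes rows and the safety aim in section 3.3.

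Separately, the sponsor should confirm whether *or* is also meant between 130 and 85 in the risk-factor row.

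The cost of the main change is one word. The eligible pool may become slightly smaller, or not change at all if staff already treat either limit as sufficient. The planned 45 participants, the waist circumference endpoint and the analysis stay as they are.
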